6.1.2. General Considerations for Analyses

Treatment period starts after the first injection of study treatment at baseline visit (Day 1) and ends after participant completed Week 16 visit or the early termination visit (ETV) (between Day 1 and Week 16). Baseline will be defined as the last available value before the first injection for efficacy and health outcome analyses. In most cases, this will be the measure recorded at baseline visit (Day 1). If the participant does not take any injection, the last available value on or

prior to randomization date will be used. Change from baseline will be calculated as the visit value of interest minus the baseline value.

For Pruritus Numeric Rating Scale (NRS), Sleep-loss due to Pruritus, and Skin Pain NRS collected via eDiary, the baseline period is the 7-day window prior to the Baseline Visit (Day 1). A participant must have responses from at least 4 of 7 days to calculate a baseline weekly mean. If a participant has 3 or fewer responses, the baseline mean value will be considered missing. eDiary data for Pruritus NRS, Sleep-loss due to Pruritus, and Skin Pain NRS are mapped to study visit per [Appendix 1](#).

For the safety analyses, the following baselines will be used. For safety analyses using a baseline period, the baseline period is defined as the time from Screening Visit to the date/time of the first injection in Treatment Period.

- Treatment-emergent adverse events (TEAEs): baseline will be all results recorded during the baseline period
- Treatment-emergent abnormal laboratory and vital signs results: baseline will be all results recorded during the baseline period
- Change from baseline to last postbaseline observation or to each scheduled postbaseline visit for laboratory and vital signs results: baseline will be the last scheduled nonmissing assessment recorded during the baseline period

The randomization to treatment groups is stratified by baseline disease severity (IGA 3 versus 4) as described in Section [5.3](#). Unless otherwise specified, the statistical analysis models for Treatment Period will adjust for baseline disease severity.

For assessments of the secondary endpoints and other binary efficacy and health outcomes endpoints, the following will be provided

- Crude proportions for each treatment group along with the 95% two-sided asymptotic (that is, not continuity corrected) CIs
- The estimated common risk difference along with 95% CIs. The common risk difference is the difference in proportions adjusted for the stratification factors as mentioned in Section [6.3](#). SAS PROC FREQ will be used for the estimates and CIs, where the CIs are calculated by using Mantel-Haenszel-Sato method (Sato 1989)
- Cochran-Mantel-Haenszel (CMH) test will be used to compare the treatment groups while adjusting for the stratification factors. The CMH p-value and the CMH adjusted odds ratio (OR) along with the 95% two-sided asymptotic (that is, not continuity corrected) CIs will be reported

Treatment comparisons of key continuous efficacy variables and health outcome variables at each postbaseline time point will be made using analysis of covariance (ANCOVA) with the following in the model: treatment group, baseline value, and stratification factors mentioned in Section [6.3](#). Type III tests for least squares (LS) means will be used for statistical comparison between treatment groups. The LS mean difference, standard error (SE), p-value, and 95% CI, unless otherwise specified, will also be reported.

Treatment comparisons of other continuous efficacy variables and health outcome variables with multiple postbaseline measurements will be made using mixed-model for repeated measures (MMRM). When MMRM is used, the model includes treatment, baseline value, visit, the interaction of the baseline value-by-visit, the interaction of treatment-by-visit, and the stratification factors mentioned in Section 6.3 as fixed factors. The covariance structure to model the within-participant errors will be unstructured. If the unstructured covariance matrix results in a lack of convergence, the heterogeneous Toeplitz covariance structure, followed by the heterogeneous autoregressive covariance structure, will be used. The restricted maximum likelihood (REML) will be used. The Kenward-Roger method will be used to estimate the denominator degrees of freedom. Type III tests for the LS means will be used for the statistical comparison; the 95% CI will also be reported.

For variables that are not collected at each postbaseline visit, data may exist at visits where the variable was not scheduled to be collected. In these situations, data from the early discontinuation visit that do not correspond to the planned collection schedule will be excluded from the MMRM analysis (Andersen and Millen 2013). Also, for by-visit summaries/displays such as boxplots, the weeks when data were not scheduled to be collected may not be displayed. However, unscheduled assessments within any defined study period will still be used in the shift analyses and for imputing values for the change from baseline to last observation carried forward (LOCF) endpoint analyses.

Unless specified otherwise, Fisher's exact test will be used for adverse events (AEs) and other categorical safety measures. Odds ratios will be created with lebrikizumab treatment as the numerator and placebo as the denominator. Continuous vital sign and laboratory values will be analyzed by an ANCOVA with treatment and baseline value in the model.

There will be no adjustment for multiple comparisons.

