Measure	Variable	Analysis Method (Section 6.1)	Population (Section 6.1.1)	Comparison/Time Point	Analysis Type
	Proportion of participants achieving IGA (0)	CMH analysis with MCMC-MI	mITT	LEB 250 mg Q2W vs PBO; Week 16 and all scheduled visits in the Treatment Period	Secondary analysis
Eczema Area and Severity Index (EASI)	Change from baseline in EASI score	ANCOVA with MCMC-MI	mITT	LEB 250 mg Q2W vs PBO; Week 16 and all scheduled visits in the Treatment Period	Secondary analysis
	Percent change from baseline in EASI score		PPS	LEB 250 mgQ2W vs PBO; Week 16 and all scheduled visits in the Treatment Period	Supplementary analysis
			mITT	LEB 250 mg Q2W vs PBO; Week 16 and all scheduled visits in the Treatment Period	Supplementary analysis
	Proportion of participants achieving EASI 75	CMH analysis with MCMC-MI	mITT	LEB 250 mgQ2W vs PBO; Week 16 and all scheduled visits in the Treatment Period	Secondary analysis
	Proportion of participants achieving EASI 90		PPS	LEB 250 mg Q2W vs PBO; Week 16 and all scheduled visits in the Treatment Period	Supplementary analysis
			mITT	LEB 250 mg Q2W vs PBO; Week 16 and all scheduled visits in the Treatment Period	Supplementary analysis
	Proportion of participants achieving EASI 50	CMH analysis with MCMC-MI	mITT	LEB 250 mg Q2W vs PBO; Week 16 and all scheduled visits in the Treatment Period	Secondary analysis

Measure	Variable	Analysis Method (Section 6.1)	Population (Section 6.1.1)	Comparison/Time Point	Analysis Type
Body Surface Area (BSA) Affected by AD	Change from baseline in BSA score	MMRM	mITT	LEB 250 mg Q2W vs PBO; Week 16 and all scheduled visits in the Treatment Period	Secondary analysis
Pruritus Numeric Rating Scale (NRS)	Change from baseline in Pruritus NRS	ANCOVA with MCMC-MI	mITT	LEB 250 mg Q2W vs PBO; Week 16 and all scheduled visits in the Treatment Period	Secondary analysis
	Percent Change from baseline in Pruritus NRS	MMRM	mITT	LEB 250 mg Q2W vs PBO; Week 16 and all scheduled visits in the Treatment Period	Supplementary analysis
	Proportion of participants achieving at least 4-point improvement in pruritus NRS in participants who had baseline pruritus NRS ≥ 4	CMH analysis with MCMC-MI	mITT participants with baseline pruritus NRS ≥ 4	LEB 250 mg Q2W vs PBO; Week 16 and all scheduled visits in the Treatment Period	Secondary analysis
		CMH analysis with NRI	mITT participants with baseline pruritus NRS ≥ 4	LEB 250 mg Q2W vs PBO; Week 16 and all scheduled visits in the Treatment Period	Supplementary analysis

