6.10.1. Primary Outcome and Methodology

The primary analysis of the study is to confirm that lebrikizumab 250 mg Q2W is the same as placebo when evaluating the booster response to the Tdap vaccine and the response to positive antibody response to MCV (Group C serum bactericidal antibodies) (proportion of participants) at Week 16 in the PPS population.

The primary estimand addresses the treatment response as directed. A 90% CI for the difference of proportion between treatment groups will be constructed using the stratified Newcombe approach (Yan and Su 2010; Kim and Won 2013) for each of the coprimary endpoints separately. Missing values will not be imputed. Descriptive statistics of antitetanus toxoid IgG antibody concentration (including the number of participants, mean, standard deviation, median, minimum, maximum, geometric mean, and coefficient of variation) and Meningococcal Group C serum rSBA titers (including the number and percentage of participants in each titer level) at Week 0, Week 12, and Week 16 will also be provided.

Primary outcomes booster response to the Tdap vaccine and the response to positive antibody response to MCV (Group C serum bactericidal antibodies), and the analysis are described in [Table KGAK.6.6](#).

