Following the implementation of MCMC-MI imputation as specified in Section 6.4.1, the 25 data sets with imputations should be set together and sorted by imputation number. The following sections describe the processes for combining inferences for the individual imputed data sets into 1 inference for reporting. All calculations are performed in SAS Software Version 9.4.

Summarize Unadjusted Response Rate

The response rates, overall and by treatment arm, and their associated SEs are computed for each imputed data set using PROC FREQ with the *riskdiff* option specified for the appropriate column in the TABLES statement. The response rates and SEs from the resulting output are combined across the 25 imputed data sets using PROC MIANALYZE, separately for each arm and the overall group.

Note that the estimate and 95% CI bounds output by PROC MIANALYZE are percentages (that is, they are in terms of the response rate). To obtain the number of responders, the estimated percentage is multiplied by the number of individuals in the analysis population and rounded to the nearest integer.

Compute Stratified Measures of Association

The common risk difference, common OR, and CMH test statistic are computed for each imputed data set using PROC FREQ with the *riskdiff* option for the appropriate column (for risk difference) and the *cmh* option (for OR and CMH test statistic) specified in the TABLES statement. Each of these analyses are stratified by geographic region, age group, and baseline disease severity via inclusion of these variables in the TABLES statement with the treatment and outcome variables.

Note that the PROC FREQ output corresponding to the Mantel-Haenszel method is used for the risk difference, and the output corresponding to the General Association statistic is used for the CMH statistic. PROC MIANALYZE is then called separately for each of these measures, with further details in the sections below.

Common Risk Difference

No transformation is necessary before using PROC MIANALYZE to combine the risk difference estimates and their associated SEs across the 25 imputed data sets. This procedure outputs an estimate of the common risk difference and the associated 95% CI bounds.

Common OR

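### For secondary and other non-co-primary binary efficacy endpoints, the per-arm 95% CIs are Wald-type under multiple imputation and become unreliable when an arm has very few responders

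*SAP*

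**What the plan says.** SAP Section 6.1.2 sets the scope: "For assessments of the secondary endpoints and other binary efficacy and health outcomes endpoints, the following will be provided". The first item under it is "Crude proportions for each treatment group along with the 95% two-sided asymptotic (that is, not continuity corrected) CIs". No other interval is given for small counts.

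SAP Appendix 3, under the heading on unadjusted response rates, explains how this works with multiple imputation: "response rates, overall and by treatment arm, and their associated SEs are computed for each imputed data set using PROC FREQ". Then: "The response rates and SEs from the resulting output are combined across the 25 imputed data sets using PROC MIANALYZE", separately for each arm and overall.

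Table KGAK.6.7 lists IGA (0), IGA (0,1), EASI 75 and EASI 90 among the binary endpoints, each at "Week 16 and all scheduled visits in the Treatment Period". The protocol's Schedule of Activities has post-baseline IGA and EASI at Weeks 4, 12 and 16. Table KGAK.6.4 adds nonresponder imputation (NRI) as a supportive method for the categorical endpoints.

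The co-primary vaccine responses are handled separately. In SAP Section 6.10.1, "A 90% CI for the difference of proportion between treatment groups will be constructed using the stratified Newcombe approach". No per-arm interval is planned for them.

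**The concern.** A Wald interval takes its width from the observed proportion. With no responders the estimated standard error is zero and the interval has no width. With a few responders the interval is symmetric about a small number, so its lower limit falls below zero and its upper limit is too low.

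Small counts are plausible here. Inclusion criteria [3] and [4] require EASI of at least 16 and IGA of at least 3, so IGA 0 at Week 4 means complete clearance within four weeks, in the placebo arm as well. SAP Section 6.4.1 sets participants who are rescued, or who stop treatment for lack of efficacy, back to their baseline values, which makes them nonresponders. At stake is how the per-arm rates are reported: a placebo rate of 0% could be shown as if known without error. The protocol (Section 9.1) plans no hypothesis testing, so intervals are its main expression of uncertainty.

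**Working it through.** **Inputs.** About 240 participants randomised 1:1, hence about 120 per arm, and 109 evaluable per arm (SAP Section 5.2). The mITT set drops two sites and its size is not stated, so n = 100, 109 and 120 per arm are used as a range. The documents give no expected rates for IGA 0 or EASI 90, so true rates of 0.5% to 5% are assumed. Coverage figures are for complete data.

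**The plan's own figures.** The SAP states Wald 90% intervals for a difference at 109 per arm. Half-width = 1.645 × √(2p(1−p)/n).
- p = 0.83: 1.645 × √(2 × 0.83 × 0.17/109) = 0.0837 (stated 0.08)
- p = 0.90: 1.645 × √(2 × 0.90 × 0.10/109) = 0.0668 (stated 0.07)

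Both reproduce. The SAP states no width or coverage for the per-arm 95% intervals.

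**Limits at small counts, n = 109.** Wald: p ± 1.96 × √(p(1−p)/n). Wilson: [p + z²/2n ± z√(p(1−p)/n + z²/4n²)] / (1 + z²/n), with z = 1.96.

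| Responders | Wald | Wilson |
|---|---|---|
| 0 | 0 to 0 | 0 to 3.4% |
| 1 | −0.9% to 2.7% | 0.2% to 5.0% |
| 2 | −0.7% to 4.4% | 0.5% to 6.4% |
| 3 | −0.3% to 5.8% | 0.9% to 7.8% |

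The Wald lower limit is negative when x < 3.84 × (1 − x/n). For n from 100 to 120 that means 1, 2 or 3 responders.

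**Coverage.** Sum the binomial probabilities of every count whose interval contains the true rate. For example, at n = 109 and a true rate of 1%, the interval misses at 0 responders (probability 0.99^109 = 0.334) and at 6 or more (0.0008). Coverage is 1 − 0.334 − 0.001 = 66%. At 3%, counts of 0 and 1 both miss low (0.036 + 0.122) and 9 or more misses high (0.006), so coverage is 84%. This is why coverage does not rise steadily with the rate.

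| True rate (assumed) | Wald, n = 109 | Wald, n = 100 to 120 | Wilson, n = 109 |
|---|---|---|---|
| 0.5% | 42% | 39–45% | 90% |
| 1% | 66% | 63–70% | 98% |
| 2% | 89% | 87–91% | 98% |
| 3% | 84% | 80–87% | 95% |
| 5% | 91% | 88–94% | 95% |

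At the rates checked from 10% to 70%, Wald coverage is 92% to 95% for n = 100 to 120.

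**Effect of imputation.** The pooled interval is estimate ± t × √T, with T = U + (1 + 1/25)B, where U is the mean within-imputation variance and B the between-imputation variance. The width is exactly zero only if all 25 data sets have no responder in that arm. Suppose one data set of the 25 has a single responder among 109:
- pooled rate = (1/109)/25 = 0.037%
- U = (1/109)(108/109)/109/25 = 3.34 × 10⁻⁶
- B = (1/109)²/25 = 3.37 × 10⁻⁶
- T = 3.34 × 10⁻⁶ + 1.04 × 3.37 × 10⁻⁶ = 6.84 × 10⁻⁶, so √T = 0.26%
- degrees of freedom = 24 × (1 + U/(1.04B))² = 91.5, t = 1.99, half-width = 0.52%
- interval: −0.48% to 0.56%

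Imputation removes the exact collapse here, but the upper limit remains far below the 3.4% that Wilson gives for 0/109.

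**The case against.** A reader might infer that every per-arm response rate in the trial has a defective interval, or that these intervals in general cover far below 95%. The documents support neither reading. Section 6.1.2 excludes the co-primary vaccine responses by its scope, categorical safety measures are compared with Fisher's exact test, and coverage is close to nominal once responses are not rare.

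Other points against the concern:

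- **The affected rows are peripheral.** IGA (0) is neither a protocol endpoint nor listed in SAP Table KGAK.4.1, and EASI 90 by visit is exploratory there. This stands, although Table KGAK.6.7 labels the IGA (0) row a secondary analysis. The protocol's binary secondary endpoints are all at Week 16, and nothing shows that any of them will be rare.
- **The rare rates are assumed.** This stands. Both arms may use low- or mid-potency topical treatment from baseline (protocol Section 6.5.1), which could raise placebo response.
- **The coverage figures are for complete data, and 109 is a per-protocol planning size.** This stands. The range of n shows that sample size matters little, but no coverage has been computed for the imputed analysis.
- **Asymptotic does not by itself mean Wald.** This is correct, since an uncorrected Wilson interval is also asymptotic. Appendix 3 settles the form for multiple imputation only. For NRI, Wald is the likely reading and not a stated one. If it is right, no responders there gives exactly (0, 0), because NRI pools nothing.
- **No decision depends on these intervals.** This stands. Arms are compared by the Mantel-Haenszel risk difference and the CMH test, and neither uses the per-arm limits.
- **The odds ratio interval also fails when an arm has no responders.** This is true, and it is a separate matter that the change below does not address.

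**Conclusion.** The concern holds within limits. Under multiple imputation, the per-arm 95% interval for secondary and other non-co-primary binary efficacy endpoints is Wald-type, and the SAP has no provision for sparse counts. If an arm's true rate is 1% or less, complete-data coverage is about 39% to 70% over n = 100 to 120. Between 2% and 5% it is about 80% to 94%. At a true rate of 1%, the chance of no responders at all is 30% (0.99^120) to 37% (0.99^100).

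This rests on assumed rates, an assumed mITT size, complete data for the coverage figures and, for NRI, an inferred interval form. The consequence is a misleading error bar on a few descriptive rows. The co-primary conclusions and the comparisons between arms do not change. It is worth correcting because the remedy needs no new data.

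**What to change.** In SAP Section 6.1.2, name the Wilson score interval for per-arm proportions and use it directly for the NRI analyses.

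In Appendix 3, specify one Wilson-type interval for imputed data, built from the pooled proportion and the total variance under Rubin's rules. Define it so that it equals the complete-data Wilson interval when the between-imputation variance is zero, including when all 25 data sets have no responders. Apply the same formula in every case, with no rule that switches method according to the data. Leave the Mantel-Haenszel risk difference and the CMH test as planned.

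The team already uses a related method: the stratified Newcombe interval for the co-primaries is built from Wilson limits. Wilson is not perfect either, with coverage of about 90% at a 0.5% rate and n = 109.

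**Cost.** SAP wording and a small amount of custom code for the imputed version, which is more than a single procedure option. SAP Version 3 was approved after the Week 16 database lock, and Section 6.16 says some statisticians had seen patient-level data by then. The change should therefore be labelled as made after the Week 16 unblinding.

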6.2. Primary and Supportive Estimands

There will be 1 estimand of interest in analyzing the primary endpoint and 3 estimands of interest in analyzing secondary endpoints for the double-blinded treatment period. For secondary endpoints, 2 types of intercurrent events (ICEs) in terms of estimating the treatment effects for the treatment period will be considered: initiation of rescue medication as defined in Appendix 2 and permanent treatment discontinuation.

6.2.1. Primary Estimand for Primary Endpoints

The primary estimand that will be used to analyze primary endpoints will include data collected for participants who are in the per-protocol set (PPS). Missing values will not be imputed.

The primary estimand (principal stratum estimand) for primary endpoints is described by the following attributes:

- Population: PPS population as defined in [Table KGAK.6.1](#)
- Endpoint: Apply to 2 primary endpoints, seroresponses to the Tdap and MCV, as defined in [Table KGAK.4.1](#)

- How to account for ICEs: The ICEs are captured through the population definition
- Population-level summary: Difference in response proportions between treatment conditions

6.2.2. Secondary and Supportive Estimands for Secondary Endpoints

The secondary estimand for secondary endpoints is a hybrid estimand representing the secondary clinical question of interest: what is the difference between treatment conditions (that is lebrikizumab vs placebo), in the target participant population, of successful response rates or means achieved after 16 weeks, without use of rescue medication, and if all participants continued with treatment except those who discontinued due to lack of efficacy?

The **secondary estimand for secondary endpoints** is described by the following attributes:

- Population: Defined through appropriate inclusion/exclusion (I/E) criteria to reflect the targeted patient population for approval
- Endpoint: Apply to all secondary endpoints
- How to account for ICEs:
 - Subjects who used rescue medication or discontinued treatment because of lack of efficacy prior to Week 16 will be considered as treatment failures, that is, nonresponder, after the ICEs. Therefore, composite strategy is used for these types of ICEs
 - For subjects who discontinued treatment because of reasons other than lack of efficacy prior to Week 16, a hypothetical strategy will be used to estimate what the treatment effect would have been if subjects continued with treatment. Therefore, hypothetical strategy is used for these types of ICEs
- Population-level summary: Difference in response proportions or means between treatment conditions

The **supportive estimand for categorical secondary endpoints** is a composite estimand as described by the following attributes:

- Population: Defined through appropriate I/E criteria to reflect the targeted patient population for approval
- Endpoint: Apply to all category secondary endpoints
- How to account for ICEs:
 - Subjects who used rescue medication or discontinued treatment prior to Week 16 will be considered as treatment failures, that is, nonresponder, after the ICEs. Therefore, composite strategy is used for these types of ICEs
- Population-level summary: Difference in response proportions between treatment conditions

The **supportive estimand for continuous secondary endpoints** is a hypothetical estimand as described by the following attributes:

- Population: Defined through appropriate I/E criteria to reflect the targeted patient population for approval
- Endpoint: Apply to all continuous secondary endpoints
- How to account for ICEs:
 - For subjects who used rescue medication or discontinued treatment prior to Week 16, a hypothetical strategy will be used to estimate what the treatment effect would have been if rescue medications were not available and all subjects adhered to the treatment. Therefore, hypothetical strategy is used for these types of ICEs
- Population-level summary: Difference in means between treatment conditions

Table KGAK.6.3 summarized secondary and its supportive estimands.

Table KGAK.6.3. Description of Secondary and Supportive Estimands for Secondary Endpoints

Estimand	Analysis Strategy for Intercurrent Events			Missing Data Imputation Method	
	Rescue Medication	Treatment Discontinuation			
		Due to Lack of Efficacy	Due to Any Other Reasons		
Primary Estimand (Hybrid)	Composite: Set to baseline	Composite: Set to baseline	Hypothetical: Set to missing	Primary analysis: MCMC-MI	
Supportive Estimand for Categorical Endpoints (Composite)	Composite: Set to nonresponder	Composite: Set to nonresponder	Composite: Set to nonresponder	NRI	
Supportive Estimand for Continuous Endpoints (Hypothetical)	Hypothetical: Set to missing	Hypothetical: Set to missing	Hypothetical: Set to missing	MMRM, LOCF	

Abbreviations: AD = atopic dermatitis; LOCF = last observation carried forward; MCMC-MI = Markov chain Monte Carlo multiple imputation; MMRM = mixed-model repeated measures; NRI = nonresponder imputation; TCS = topical corticosteroids.

